#### 4.8.1.3 Precautions for Women of Childbearing Potential

The nonclinical findings of increased late-stage pregnancy loss and early infant deaths/euthanasia in nivolumab-exposed pregnant monkeys suggest a potential risk to human pregnancy if there is continued treatment with nivolumab during pregnancy. However, cases of human in-utero exposure to nivolumab (involving the fetuses of female subjects receiving nivolumab) were reported. Given the potential risk suggested by preliminary data from nonclinical and clinical data, dosing during pregnancy will continue to be prohibited. In addition, women of childbearing potential (WOCBP) receiving nivolumab will be instructed to adhere to contraception for a period of 5 months after the last dose of nivolumab. WOCBP also must not donate eggs while on treatment or for 5 months after the last dose of nivolumab.

These durations have been calculated using the upper limit of the half-life for nivolumab (~25 days) and are based on the recommendation that WOCBP use contraception for 5 half-lives after the last dose of nivolumab. Females should not breastfeed while receiving nivolumab and for any subsequent protocol-specified period.

Female subjects should start using birth control from study Visit 1 throughout the study period up to 5 months after the last dose of study therapy.

Women of childbearing potential (WOCBP) must have a negative serum or urine pregnancy test (urine pregnancy test: minimum sensitivity 25 IU/L or equivalent units of human chorionic gonadotropin [hCG]) within 14 days prior to the start of study drug. Women must not be breastfeeding. Females of nonchildbearing potential are those who are postmenopausal greater than 1 year or who have had a bilateral tubal ligation or hysterectomy. Females of childbearing potential must agree to use 2 effective contraceptive methods during the study and for 5 months following the last dose of nivolumab.

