#### 4.8.1.4 Use in Pregnancy

If a subject inadvertently becomes pregnant while on treatment with nivolumab, the subject will immediately be removed from the study. The site will contact the subject at least monthly and document the subject's status until the pregnancy has been completed or terminated. The outcome of the pregnancy will be reported to BMS without delay and within 24 hours to the Sponsor-Investigator and

within 2 business days of investigator knowledge if the outcome is a serious adverse experience (e.g., death, abortion, congenital anomaly, or other disabling or life-threatening complication to the mother or newborn).

The study investigator will make every effort to obtain permission to follow the outcome of the pregnancy and report the condition of the fetus or newborn to BMS. If a male subject impregnates his female partner the study personnel at the site must be informed immediately and the pregnancy reported to BMS and followed as described above.

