## 7.2 Exclusion Criteria

- 1. Receipt of intervening systemic therapy after CAR T-cell infusion
- 2. History of another primary malignancy that has not been in remission for at least 1 year (with the exception of non-melanoma skin cancer, curatively treated localized prostate cancer, curatively treated superficial bladder cancer and cervical carcinoma in site on biopsy or a squamous intraepithelial lesion on PAP smear)
- 3. Active hepatitis B, hepatitis C at time of screening
- 4. Known (HIV) seropositivity
- 5. Subjects with uncontrolled infection
- 6. Concurrent use of other anticancer agents or experimental treatments
- 7. Active autoimmune disease requiring immunosuppressive therapy with the exception of vitiligo and autoimmune alopecia
- 8. Known active CNS involvement
- 9. Subjects with a condition requiring systemic treatment with either corticosteroids ( $>$ 10 mg daily prednisone equivalent) or other immunosuppressive medications within 14 days of study drug administration. Inhaled or topical steroids, and adrenal replacement doses are permitted in absence of active autoimmune disease
- 10. Known history of any active infectious pneumonitis
- 11. Presence of acute or chronic graft-versus-host disease (GVHD) requiring active treatment unless limited to skin involvement and managed with topical steroid therapy alone
- 12. Has active cytokine release syndrome
- 13. Pregnancy or breastfeeding: Women of childbearing potential (WOCBP) must have a negative serum or urine pregnancy test (urine pregnancy test: minimum sensitivity 25 IU/L or equivalent units of human chorionic gonadotropin [hCG]) within 14 days of the first dose of study drug.

Women must not be breastfeeding. Females of nonchildbearing potential are those who are postmenopausal greater than 1 year or who have had a bilateral tubal ligation or hysterectomy. Females of childbearing potential and males who have partners of childbearing potential must agree to use 2 effective contraceptive methods during the study and for 8months following the last dose of nivolumab.

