### Figure 1. Study Design

The study will be conducted as a single arm phase II trial. After 2 cycles, an interim response assessment will be conducted to evaluate for early progression. Subjects with disease progression at that assessment will be discontinued from study treatment. Subjects will undergo disease-specific monitoring for response, as outlined in Section 9.5, during treatment on study.

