## 9.6 Subject Withdrawal/Discontinuation Criteria

Subjects may withdraw consent at any time for any reason or be dropped from the trial at the discretion of the investigator should any untoward effect occur. In addition, a subject may be withdrawn by the investigator for significant subject noncompliance with protocol requirements, or for administrative and/or other safety reasons. Subjects who require cessation of study therapy but do not withdraw consent may remain in standard follow-up for up to 5 years.

A subject must be discontinued from the trial for any of the following reasons:

- The subject or legal representative (such as a parent or legal guardian) withdraws consent.
- Confirmed radiographic disease progression
- Unacceptable adverse experiences
- Intercurrent illness that prevents further administration of treatment
- Investigator's decision to withdraw the subject
- The subject has a confirmed positive serum pregnancy test
- Noncompliance with trial treatment or procedure requirements
- The subject is lost to follow-up
- Administrative reasons

The End of Treatment and Follow-up visit procedures are listed in Appendix A (Study Calendar) and Section 11.1.5 (Visit Requirements). After the end of treatment, each subject will be followed for 30 days for adverse event and 90 days for serious adverse event monitoring. Subjects may have post-treatment follow-up up to 5 years per routine standard of care for survival and disease status.

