## 10.0 CLINICAL AND LABORATORY EVALUATIONS

### 10.1 Schedule/Timing of Events (See Appendix A, Study Calendar)

#### 10.1.1 Screening Evaluations (Day -28 to Day -1)

- Research Consent, HIPAA
- Medical History, Including:
  - Hematologic, cytogenetic, flow cytometric, and histologic findings at time of diagnosis and at time of enrollment on the study
  - Prior therapies and response to therapies
- Physical Examination
- ECOG Performance Status (See Appendix B)

- Chemistries, Hematology
  - CBD (to include: white blood cell count, red blood cell count, hemoglobin, hematocrit, platelet count, absolute neutrophils, lymphocytes, monocytes, eosinophils, basophils, immature granulocytes)
  - Renal/Hepatic Function Panel (to include: sodium, potassium, chloride, total carbon dioxide, anion gap, glucose, urea nitrogen, creatinine, total protein, albumin, total bilirubin, direct bilirubin, calcium, phosphate, AST (GOT), Alkaline phosphatase, ALT (GPT), eGFR)
  - Magnesium, Lactate Dehydrogenase
- C-reactive Protein (CRP), Ferritin
- Uric Acid
- Serum or urine HCG within 14 days of cycle 1, day 1
- Coagulation Panel (To include INR, PT, PTT)
- Urinalysis
- T3, FT4, TSH
- Archival pre-treatment tumor biopsy (if available)
- Disease Specific:
  - Multiple Myeloma
    - Serum free light chain (SFLC) Assessment to include kappa to lambda ratio
    - SPEP with immunofixation
    - Bence Jones quantification, only in subjects for whom urinary Bence Jones quantitation represents best marker of disease
    - PET/CT (only amongst patients in whom plasmacytoma is the only measurable site of disease)
    - Bone marrow aspirate and biopsy, to include: histopathology, flow cytometry, FISH, and conventional cytogenetics
  - Non-Hodgkin Lymphoma, CLL
    - PET/CT and Diagnostic CT of the chest, abdomen, and pelvis. Diagnostic CT of neck only if palpable lymphadenopathy present
    - CLL Only: Bone marrow aspirate and biopsy, to include morphology, flow cytometry, FISH, cytogenetics

## 10.2 On Study Evaluations, Cycle 1

- Days 1
  - History and Physical Exam
  - Performance Status
  - Vital Signs (Including Temperature, Blood Pressure, Heart Rate, Oxygen Saturation)
  - Chemistry/Hematology
    - CBD
    - Renal/Hepatic Function Panel
    - Magnesium and LDH
  - CRP, Ferritin
  - Uric Acid

- Coagulation Panel
- T3, FT4, TSH
- Research Samples
  - Blood
    - Cytokines
    - Exploratory laboratory specimen
- Disease Specific:
  - Multiple Myeloma

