# 11.0 STUDY PROCEDURES

## 11.1 Study Procedures

The Study Calendar in Appendix A summarizes the trial procedures to be performed at each visit. Individual trial procedures are described in detail below. It may be necessary to perform these procedures at unscheduled time points if deemed clinically necessary by the investigator.

Furthermore, additional evaluations/testing may be deemed necessary by the investigator and/or BMS for reasons related to subject safety. In some cases, such evaluation/testing may be potentially sensitive in nature (e.g., HIV, Hepatitis C, etc.), and thus local regulations may require that additional informed consent be obtained from the subject. In these cases, such evaluations/testing will be performed in accordance with those regulations.

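### Pregnancy is a mandatory stop, but hCG is scheduled only at screening: require a negative test within 3 days before every dose, including the first (low priority, cheap)

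*Combined protocol and SAP*

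**What the plan says.** Section 4.8.1.3 states that "dosing during pregnancy will continue to be prohibited". Section 4.8.1.4 gives the consequence: "If a subject inadvertently becomes pregnant while on treatment with nivolumab, the subject will immediately be removed from the study". Section 9.6 lists as a ground for mandatory discontinuation "The subject has a confirmed positive serum pregnancy test", and Section 12.0 names pregnancy among the reasons for which treatment must end.

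The testing rule is the same wherever it appears. Section 7.2 requires that "Women of childbearing potential (WOCBP) must have a negative serum or urine pregnancy test" within 14 days of the first dose, and Section 4.8.1.3 sets the same window. Section 10.1.1 lists "Serum or urine HCG within 14 days of cycle 1, day 1". The pregnancy-test row of Appendix A is marked under Screening only. The visit lists in Sections 10.2 to 10.6 contain no hCG. Footnote 4 of Appendix A limits the test to women of childbearing potential and says that, during the trial, pregnancy comes to light by verbal report.

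Other controls are in place. Two contraceptive methods are required during the study (4.8.1.3, 7.2). History and physical examination are listed for Day 1 of every cycle (10.2 to 10.5). Section 11.1 notes that "It may be necessary to perform these procedures at unscheduled time points if deemed clinically necessary by the investigator", and lets the investigator or the funder ask for further testing for safety reasons. Section 11.1.3 requires laboratory results to be reviewed and judged acceptable before each dose, but hCG is not among the tests scheduled for those visits.

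**The concern.** A ban on dosing in pregnancy protects only if the site knows of the pregnancy. Verbal report cannot reveal one that the subject does not know about. The Section 9.6 trigger is a serum result that no on-treatment visit is scheduled to produce.

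The stake is participant safety. From late pregnancy losses and early infant deaths in exposed monkeys, Section 4.8.1.3 infers a potential risk to human pregnancy when treatment is continued. Continued treatment is what a pre-dose test would interrupt. The same section records that human in-utero exposures have been reported.

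**Working it through.** The plan states no figure to reproduce. The check is a comparison of schedules, followed by simple arithmetic on the size of the gap.

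**1. Scheduled tests per woman of childbearing potential.** Screening: 1. Cycle 1 Day 1 onward, including end of treatment: 0 (Sections 10.2 to 10.6 and the Appendix A row agree).

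**2. Number of doses.** Dosing is every 28 days (Section 9.1).
- Short case: progression at the 8-week assessment. The text under Figure 1 says "Subjects with disease progression at that assessment will be discontinued from study treatment". Doses fall on days 0 and 28, so 2 doses.
- Long case: the synopsis gives 9 months, about 274 days. Doses on days 0, 28, ..., 252 make 10. Treatment is open-ended until progression or toxicity, so 10 is not a maximum. The long case is also not typical: Section 3.1 cites a median overall survival of 5.1 months in CAR-T non-responders.

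**3. Age of the last scheduled test at dose k.** At most 14 + 28(k − 1) days, ignoring the ±3-day visit windows.
- Dose 1: 14 days.
- Dose 2: 14 + 28 = 42 days.
- Dose 10: 14 + 252 = 266 days.
- With a test required before every dose: at most 3 days throughout.

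The gap therefore includes dose 1. It is narrower there because one test precedes that dose.

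**4. Doses at stake per unrecognised pregnancy.** If dosing continues through a window of w days in which the pregnancy is detectable but unrecognised, the average number of doses in it is w/28. Assuming 2, 4 or 8 weeks gives 14/28 = 0.5, 28/28 = 1 and 56/28 = 2. These overstate the exposure of anyone taken off early: the short case has only one dose after the first. With a test up to 3 days before dosing, a dose is still given only if the pregnancy becomes detectable in those days: at most 3/28 = 0.11, and zero for a same-day test.

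**5. What the test cannot do.** With the 25-day upper half-life in Section 4.8.1.3 and simple exponential decay, 2^(−28/25) = 0.46 of the previous dose remains after 28 days. A test prevents further dosing but cannot undo earlier exposure.

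**6. Expected frequency.** Section 16.5 plans 9 female subjects of 20. The number of childbearing potential and the pregnancy rate are not given. The inputs here are assumptions: 1 to 4 such women, 2 to 9 months on treatment, 1% to 5% pregnancies per woman-year.
- Low: 1 × (2/12) × 0.01 = 0.0017.
- High: 4 × (9/12) × 0.05 = 0.15.
- All 9 women at the worst inputs: 9 × (9/12) × 0.05 = 0.34.

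Only the unrecognised share of these counts. Treatment beyond 9 months would raise them in proportion.

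**The case against.** The strongest reply is that this is a deliberate and disclosed choice. Footnote 4 says how pregnancy is identified on trial. Two-method contraception, Day 1 history and examination, and discretionary testing stand behind it. Nothing in the documents requires a test before each dose. The expected benefit is close to zero and rests on assumed rates, and many subjects will stop early. The link to harm is also loose: the animal findings concern late loss and infant death, and the documents give no risk for one or two doses in early pregnancy.

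Most of this stands, and it sets the priority. It does not close the gap. Contraception lowers the frequency of pregnancy but does not detect one. History, examination and discretionary testing all need a sign or a suspicion.

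Three stronger readings are tempting and should be resisted.
- A reader might infer that the protocol contradicts itself or cannot apply its own stopping rule. It does not: the testing schedule agrees in every place, and the serum confirmation in Section 9.6 can be obtained by an unscheduled test after a report.
- A reader might infer that exposed pregnancies are to be expected. The documents give no rate to support that, and the illustrative range is well below one.
- A reader might infer a threat to the primary analysis. Neither the gap nor the fix changes the response endpoint, the alpha or the power.

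Sections 4.8.1.3 and 7.2 do differ on how long contraception continues after the last dose (5 against 8 months). Both require two methods during the study, so this point is unaffected.

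**Conclusion.** The point holds as a low-priority, inexpensive safety improvement. Certain from the documents: pregnancy is a mandatory stop, the only scheduled hCG is at screening, and an unrecognised pregnancy could be dosed at cycle 1 or later without departing from the plan. Not certain: how often. The expected number of affected subjects is taken to be well below one, on assumed counts and rates. The case for acting rests on the seriousness of the possible outcome against a very small cost, not on expected numbers. No relative reduction in exposure should be claimed on so small a base.

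**What to change.** For women of childbearing potential, require a negative hCG within 3 days before Day 1 of every cycle, including cycle 1, and on the dosing day where the result can be back in time. Use a serum test, or a urine test with serum confirmation of any positive, so that a positive leads directly to the Section 9.6 criterion. Make the negative result a condition of infusion under the Section 11.1.3 review, which already allows chemistry and hematology within 3 days before Day 1. The 14-day eligibility test can stay. Amend Sections 10.2 to 10.5, the Appendix A pregnancy-test row (Cycle 1 Day 1, Cycle 2 Day 1, Cycles 3-6 Day 1, Cycle 7+ Day 1) and footnote 4.

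Cost: an amendment to four visit lists, one calendar row and one footnote, and one assay per cycle per such woman on blood already drawn. That is about 10 assays over 9 months including cycle 1, and more if treatment runs longer. If all 9 planned female subjects were of childbearing potential and treated for 9 months, the total would be 9 × 10 = 90. An occasional dose would be delayed while a positive is resolved. No new visit or needle is needed.

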#### 4.8.1.4 Use in Pregnancy

If a subject inadvertently becomes pregnant while on treatment with nivolumab, the subject will immediately be removed from the study. The site will contact the subject at least monthly and document the subject's status until the pregnancy has been completed or terminated. The outcome of the pregnancy will be reported to BMS without delay and within 24 hours to the Sponsor-Investigator and

within 2 business days of investigator knowledge if the outcome is a serious adverse experience (e.g., death, abortion, congenital anomaly, or other disabling or life-threatening complication to the mother or newborn).

The study investigator will make every effort to obtain permission to follow the outcome of the pregnancy and report the condition of the fetus or newborn to BMS. If a male subject impregnates his female partner the study personnel at the site must be informed immediately and the pregnancy reported to BMS and followed as described above.

#### 4.9 Risk / Benefit of PD-1 Inhibitors in Multiple Myeloma

Checkpoint inhibitors – principally PD-1 and PD-L1 inhibitors – have been studied extensively in multiple myeloma. Studies of PD-1 inhibitors as a monotherapy did not show substantial anti-tumor activity, but also did not have any concerning safety signals. A Phase 1b study of nivolumab, an anti-PD-1 antibody, in patients with relapsed or refractory hematologic malignancy patients, included 27 patients with MM. With respect to safety, the MM cohort appeared to have a decreased risk of any grade adverse event (AE) as compared with the B-Cell NHL and T-CELL NHL patients (52% compared with 71% and 74%, respectively), and a decreased rate of grade  $\geq 3$  AEs (19% vs 26% and 22%, respectively). The study also showed minimal single agent efficacy, with an overall response rate (ORR) of 4% (1 complete response), with all other patients having stable disease. The KEYNOTE-013 trial was a multi-center Phase 1b study of pembrolizumab, a PD-1 antibody, in patients with hematologic malignancies. The study accrued 30 patients with MM; 40% of patients had any treatment-related AE (TRAE), and only 1 patient experienced a grade  $\geq 3$  AE (3.3%). There were no grade 4 or 5 TRAEs. The study did not show evidence for anti-tumor activity, with an ORR of 0%; the majority of patients had stable disease (56.7%). Taken together, phase 1 studies of PD-1 inhibitors in MM show an acceptable safety profile in line with that seen in other cancers, but little evidence for single agent activity.

Despite the discouraging results seen with PD-1 inhibitor monotherapy in MM, there was some theoretical evidence that combination of immunomodulatory agents (IMiDs) such as lenalidomide or pomalidomide with PD-1 inhibition may be synergistic, leading to the development of several phase 3 trials. However, these trials were all put on hold in 2017 due to an interim analysis that showed an increased risk of death in MM patients on the experimental arm of these trials. KEYNOTE-185 was a randomized phase 3 trial comparing pembrolizumab, lenalidomide, and dexamethasone, to lenalidomide and dexamethasone for patients with newly diagnosed MM. On July 3, 2017, the FDA halted the trial due to an imbalance in deaths in the experimental arm – with 6 treatment related deaths in the experimental arm, and 2 in the control arm. The KEYNOTE-183 trial was a randomized study in relapsed/refractory MM, comparing pomalidomide, pembrolizumab, and dexamethasone, to pomalidomide and dexamethasone. This trial was also halted early due to an imbalance of deaths, with 4 treatment-related deaths in the study arm, and no deaths in the control arm. Taken together, these trials suggest an adverse risk benefit ratio for combining PD-1 inhibitors with IMiDs in patients with MM.

Despite these findings, there is still good rationale for novel combinations of PD-1 inhibitors with other immunotherapy based approaches. An example of an unmet need where PD-1 inhibitors could be considered is in CAR T cell therapy. The phase 1 study of bb2121, a CAR T cell therapy targeting BCMA in MM, showed a median progression-free survival of 11.8 months; CAR T cell expansion and persistence was associated with responses. Inevitably, however, all patients will relapse, and potentially using a PD-1 inhibitor for patients who relapse could result in responses due to persistent circulating CAR T cells, as has been seen in other hematologic malignancies. Thus, there is good

rationale for using PD-1 inhibition as a monotherapy in this setting for MM patients, given that there were no adverse safety signals with PD-1 inhibitors seen when given as monotherapy.

## **5.0 OVERVIEW OF CLINICAL TRIAL**

### **5.1 Study Design**

This is a pilot study of nivolumab, 480 mg IV every 4 weeks, for patients with relapsed or persistent disease after treatment with CAR T-cell therapies.

### **5.2 Primary Endpoint**

- Best overall response rate, as assessed by disease-specific guidelines:
  - Multiple Myeloma – International Myeloma Working Group response criteria (See Appendix F)
  - Non-Hodgkin Lymphoma – Response assessment will be based on the Lugano Criteria (See Appendix D)
  - Chronic Lymphocytic Leukemia – Response assessment based on the IWCLL Criteria (See Appendix E)

